**Figure 12-1 Testing strategy for symptomatic dermographism and cold urticaria**

For symptomatic dermographism and cold urticaria CINDU cohort, the hypotheses are mapped into two families.

The first family consists of four hypotheses:  $H_{11}$ ,  $H_{12}$ ,  $H_{21}$ , and  $H_{22}$ . These four hypotheses form two branches such that hypotheses within a same branch correspond to the same ligelizumab dose regimen (72 mg q4w or 120 mg q4w). In essence, the type-I-error probability will be equally split for both branches of hypotheses and within each branch the hypotheses are tested sequentially as follows:

The initial alpha level for each branch is set to  $\alpha/2=0.0125$  (one-sided). The first hypothesis ( $H_{11}$  and  $H_{12}$ ) is tested with  $\alpha/2=0.0125$  (one-sided) of high/low dose ligelizumab versus placebo regarding the primary endpoint. If either of the hypotheses is rejected, the corresponding second hypotheses ( $H_{21}$  and/or  $H_{22}$ ) of high/low dose ligelizumab versus placebo regarding the secondary endpoint on complete response is tested with  $\alpha/2$ .

In the first family, the testing within each dose is strictly hierarchical: the secondary endpoint on complete response will only be assessed if efficacy was shown previously for the primary endpoint. If efficacy is shown for both the primary and the secondary endpoint for one of the doses, the associated weight is passed on to the other dose.

The second family consists of  $H_{31}$  and  $H_{32}$ , will only be tested if all four hypotheses in the first family are rejected. The initial alpha level will be equally split (i.e. is set to  $\alpha/2=0.0125$ , one-sided) for each hypothesis. If either of the hypotheses is rejected, the associated weight is passed on to the other dose, so that other hypothesis is tested with  $\alpha$ .

### Testing strategy for cholinergic urticaria

The following null hypotheses ( $H_0$ ) will be tested against the respective alternative hypotheses ( $H_A$ ) in a closed testing procedure (Bretz et al 2009), thus controlling the family-wise type I error which is set to 0.025 (one-sided) for cholinergic urticaria.

#### Primary endpoint

Itch NRS change from baseline at Week 12

$$H_{01}: \mu_{\text{ligelizumab}} \geq \mu_{\text{Placebo}} \text{ versus } H_{A1}: \mu_{\text{ligelizumab}} < \mu_{\text{Placebo}}$$

where  $\mu$  is the mean change from baseline in itch NRS following the pulse-controlled ergometry test at Week 12, as described in [Section 2.1](#).

#### Secondary endpoints

- proportion of participants achieving complete response in itch NRS (itch NRS=0) following the pulse-controlled ergometry test at Week 12

$$H_{02}: \pi_{\text{ligelizumab}}^{\text{itch}} \leq \pi_{\text{Placebo}}^{\text{itch}} \text{ versus } H_{A2}: \pi_{\text{ligelizumab}}^{\text{itch}} > \pi_{\text{Placebo}}^{\text{itch}}$$

where  $\pi^{\text{itch}}$  is the proportion of participants achieving complete response in itch NRS at Week 12, as described in [Section 2.2](#).

[figure not shown]
- proportion of participants achieving complete response in physician global assessment of severity of hives (PGA hive score =0) following the pulse-controlled ergometry test at Week 12

$H_{03}: \pi^{hive}_{ligelizumab} \leq \pi^{hive}_{Placebo}$  versus  $H_{A3}: \pi^{hive}_{ligelizumab} > \pi^{hive}_{Placebo}$

where  $\pi^{hive}$  is the proportion of participants achieving complete response in PGA hive score=0 at Week 12, as described in [Section 2.2](#).

**Figure 12-2 Testing strategy for cholinergic urticaria**

**120 mg vs. PBO**

For cholinergic urticaria, the hypotheses are tested sequentially in a fix order as follows:

The initial alpha level is set to  $\alpha=0.025$  (one-sided) for the first hypothesis (H1) of ligelizumab 120 mg q4w versus placebo regarding the primary endpoint. If H1 is rejected, the second hypothesis (H2) of ligelizumab versus placebo regarding the secondary endpoint on complete response in itch NRS is tested with  $\alpha$ . If H2 is rejected, the third hypothesis (H3) of ligelizumab versus placebo regarding the secondary endpoint on complete response in physician global assessment of severity of hives is tested with  $\alpha$ .

**12.5.1 Efficacy [REDACTED] endpoint(s)**

Efficacy endpoints other than the primary and secondary endpoints are detailed in [Section 12.6](#).

**12.5.2 Safety endpoints**

The following applies to all three subtypes of CINDU (i.e. symptomatic dermographism, cold urticaria, and cholinergic urticaria).

For all safety analyses (i.e. AEs, laboratory data, vital signs, and ECG), the safety set will be used. All data will be included in the analysis regardless of rescue medication use. All listings and tables will be presented by treatment group.

## **Adverse events**

All information obtained on AEs will be displayed by treatment group (or sequence) and participant.

Treatment emergent AEs will be summarized by actually received treatment.

Treatment emergent AEs (TEAE) are defined as:

- Events started after the first dose of study treatment (ligelizumab) in this study and within 16 weeks of last dose of study treatment
- Events present prior to the first dose of study treatment (ligelizumab) in this study but:
  1. increased in severity based on preferred term (e.g. worsening of headache),
  2. same PT but increased severity (e.g. from mild to moderate),
  3. same PT but increase in seriousness (from non-serious AE to SAE; if already a SAE from medical significant to LT/fatal)and within 16 weeks after the last dose of the study treatment.

The number (and percentage) of participants with treatment emergent AEs will be summarized in the following ways:

- by treatment, primary system organ class and preferred term.
- by treatment, primary system organ class, preferred term and maximum severity.
- by treatment, Standardized MedDRA Query (SMQ) and preferred term.

Separate summaries will be provided for study medication related AEs, death, SAEs, other significant adverse events leading to treatment discontinuation.

The number (and proportion) of participants with treatment emergent AEs of special interest (AESI) will be summarized by treatment.

The number (and proportion) of participants with treatment emergent AEs related to other safety topics such as events related to “liver toxicity” will be summarized by treatment.

A participant with multiple AEs within a primary system organ class is only counted once towards the total of the primary system organ class.

For the placebo-ligelizumab treatment group, treatment-emergent AEs will be counted separately for the placebo treatment and ligelizumab treatment.

## **Vital signs**

All vital signs data will be listed by treatment group, participant, and visit/time and if ranges are available, abnormalities will be flagged. Summary statistics will be provided by treatment, and visit/time and separately in adults and adolescents.

### **12-lead ECG**

All ECG data will be listed by treatment group, participant and visit/time. Newly occurring or worsening abnormalities will be flagged.

For ECGs, a notable QTc value is defined as a QTcF interval of greater than 450 ms for males or greater than 460 ms for females – all such ECGs will be flagged by the Central CRO's cardiologist and require assessment for clinical relevance by the investigator. For adolescent participants, the Central CRO will use age-and gender-specific reference values.

### **Clinical laboratory evaluations**

All laboratory data will be listed by treatment group, participant, and visit/time and if normal ranges are available abnormalities will be flagged.

Descriptive summary statistics for the change from baseline to each study visit will be presented. These descriptive summaries will be presented by laboratory test and treatment group. Change from baseline will only be summarized for participants with both baseline and post baseline values. For categorical parameters, frequencies by categories at each visit will be summarized.

Shift tables using the low/normal/high/ (low and high) classification will be used to compare baseline to the worst on-treatment value.

### **Other safety evaluations**

[REDACTED]

[figure not shown]
[REDACTED]

[REDACTED]

[REDACTED]

### **Resource utilization**

Data relating to resource utilization will be used for the purpose of economic evaluation and will be carried out and reported as a separate activity.

## 12.7 Interim analyses (Futility analysis)

A final analysis will be performed after all participants have completed Week 36 (or discontinued prior to Week 36). Formal testing of the primary endpoint with full level alpha will be performed at the primary analysis time point.

Due to the low prevalence of cholinergic urticaria, an interim futility analysis may be conducted in case there is an obvious difference in recruitment speed in the three cohorts. In other words, this interim futility analysis would be triggered when approximately 50% of randomized participants in the cholinergic urticaria cohort have completed the Week 12 visit while 100% of randomized participants in the symptomatic dermographism and cold urticaria cohorts have completed the Week 12 visit. During this analysis, there will be no decision rules applied for the symptomatic dermographism and cold urticaria cohort. This analysis will be conducted to assess whether efficacy met a pre-specified level only for the cholinergic urticaria cohort.

Depending on the outcome of the futility analysis, further recruitment in cholinergic urticaria subtype may be stopped or continued as planned. Participants who have already been enrolled in the study prior to the futility analysis will continue to remain in the study.

Futility analysis results will be evaluated by the DMC based on calculated predictive probabilities of the primary estimand (see [Section 2](#)) for cholinergic urticaria. Details of the calculations and the associated thresholds will be described in the DMC Charter and its associated analysis plan. Additional analyses on the secondary estimand (see section 2) and safety will also be performed to assist in the futility evaluation, as planned in the DMC charter.

## 12.8 Sample size calculation

### Symptomatic dermographism

The sample size justification is based on change from baseline in Total Fric Score and achievement of complete response in FricTest®4.0 at Week 12.

### Cold urticaria

The sample size justification is based on change from baseline in CTT (in response to TempTest®4.0) and achievement of complete response in TempTest®4.0 at Week 12.

### Cholinergic Urticaria

The sample size justification is based on change from baseline in itch NRS in response to the pulse-controlled ergometry test and achievement of complete response in itch NRS (itch NRS=0) at Week 12.

For symptomatic dermographism and cold urticaria, participants will be randomized in a 2:2:1:1 ratio to ligelizumab 72 mg q4w, ligelizumab 120 mg q4w, placebo - ligelizumab 120 mg q4w, and placebo - ligelizumab 72 mg q4w, respectively. In other words, participants are randomly assigned to ligelizumab 72 mg q4w, ligelizumab 120 mg q4w, and placebo group with a 1:1:1 ratio in the placebo-controlled period (i.e. up to Week 12). For cholinergic urticaria, participants will be randomized in a 1:1 ratio to ligelizumab 120 mg q4w and placebo - ligelizumab 120 mg q4w.

All sample size calculations were performed with SAS 9.4 PROC POWER.

Based on simulation studies, the sample sizes calculated below for each of the three CINDU cohorts are sufficient to maintain the power of overall multiple testing strategy (at least 90%) for the primary endpoint (see [Section 2.1](#)) and the first secondary endpoint (i.e. complete response rate following the FricTest®4.0 for symptomatic dermographism, complete response rate following the TempTest®4.0 for cold urticaria, and complete response rate in itch NRS following the pulse-controlled ergometry test for cholinergic urticaria) through the recycled alpha. Detailed simulation results on power with all endpoints in the testing strategy (see [Section 12.5](#)) are provided in the statistical analysis plan.

Data from each subtype is analyzed separately. Hence if sample size is not achieved for one of the subtypes, this will not impact the analysis for the other subtypes. The overall population (adolescent and adult participants) will be considered for the primary and secondary analyses.

## 12.8.1 Primary endpoint(s)

### Symptomatic Dermographism

Since two ligelizumab dose regimens will be tested versus placebo with respect to the primary endpoints (change from baseline in Total Fric Score at Week 12), the type-I-error will be split to 1.25% one-sided for each comparison.

Assuming the treatment difference in change from baseline to Week 12 in Total Fric Score is at least 1.3 in favor of the ligelizumab group, and a standard deviation of approximately 1.7, a sample size of approximate 56 participants per group and a drop-out rate of 10% provides 93.7% power to show that the primary analysis based on a two-sample t-test will be statistically significant at the one-sided 1.25% significance level (SAS 9.4, PROC POWER, difference in two sample means).

Mean changes from baseline in Total Fric Score of -0.6 (standard deviation: 1.4) in placebo group, -1.78 (standard deviation: 1.66) in omalizumab 150 mg group, and - 2.0 (standard deviation: 1.67) in omalizumab 300 mg group have been reported in [Maurer et al 2017](#).

**Table 12-1 Sensitivity of power to changes in assumptions (Symptomatic Dermographism)**

True treatment difference ligelizumab vs placebo (Total Fric Score)	SD (Total Fric Score)	Power for primary endpoint (one-sided $\alpha = 1.25\%$ ), for N= 56 per arm		
		With 5% drop-out rate	With 10% drop-out rate	With 15% drop-out rate
1.5	2	94.2%	92.8%	91.1%
1.3	2	85.6%	83.3%	80.7%
1.3	1.7	95.0%	93.7%	92.1%
1	1.3	95.3%	94.0%	92.5%

SD=Standard Deviations

### Cold Urticaria

Since two ligelizumab dose regimens will be tested versus placebo with respect to the primary endpoints (change from baseline in critical temperature thresholds (CTT) at Week 12), the type-I-error will be split to 1.25% one-sided for each comparison.

Assuming the treatment difference in change from baseline to Week 12 in CTTs is at least 10°C in favor of the ligelizumab group, and a standard deviation of approximately 8°C, a sample size of approximate 34 participants per group a drop-out rate of 10% provides >99% power to show that the primary analysis based on a t-test will be statistically significant at the one-sided 1.25% significance level (SAS 9.4, PROC POWER, difference in two sample means).

Mean changes from baseline in CTT of -0.3°C (standard deviation: 3.9°C) in placebo group, CTT of -10.6°C (standard deviation: 7.6°C) in omalizumab 150 mg group, and CTT of -10.4°C (standard deviation: 9.4°C) in omalizumab 300 mg group have been reported in [Metz et al 2017](#).

**Table 12-2 Sensitivity of power to changes in assumptions (cold urticaria)**

True treatment difference ligelizumab vs placebo (°C)	SD (°C)	Power for primary endpoint (one-sided $\alpha = 1.25\%$ ) for N= 34 per arm		
		With 5% drop-out rate	With 10% drop-out rate	With 15% drop-out rate
11	10	98.1%	97.3%	96.2%
10	10	95.3%	93.9%	92.1%
10	9	98.3%	97.5%	96.5%
8	8	95.3%	93.9%	92.1%

SD=Standard Deviation

### Cholinergic Urticaria

Assuming the treatment difference in change from baseline to Week 12 in itch NRS following the pulse-controlled ergometry test is at least 1.65 in favor of the ligelizumab 120 mg q4w group, and a standard deviation of approximately 3.0, a sample size of approximate 79 participants per group and a drop-out rate of 10% provides 90.2% power to show that the primary analysis based on a two-sample t-test will be statistically significant at the one-sided 2.5% significance level (SAS 9.4, PROC POWER, difference in two sample means).

Median pre-treatment itch VAS of 60 (25th percentile=40, 75th percentile=80) and median post-treatment itch VAS of 30 (25th percentile=20, 75th percentile=70) in the overall population after 4 doses of omalizumab 300 mg have been reported in [Gastaminza et al](#).

**Table 12-3 Sensitivity of power to changes in assumptions (cholinergic urticaria)**

True treatment difference ligelizumab vs placebo (itch NRS)	SD (itch NRS)	Power for primary endpoint (one-sided $\alpha = 2.5\%$ ) for N= 79 per arm		
		With 5% drop-out rate	With 10% drop-out rate	With 15% drop-out rate
1.5	2.5	95.5%	94.4%	93.2%
1.5	3.0	86.0%	84.1%	81.9%
1.65	3	91.7%	90.2%	88.5%
1.8	2.5	99.2%	98.9%	98.5%

SD= Standard Deviation

**Table 12-4 Sensitivity of required sample size (per arm) to changes in assumptions for different targeted statistical power (cholinergic urticaria)**

Sample size required
----------------------

True treatment difference ligelizumab vs placebo (itch NRS)	SD (itch NRS)	Targeted statistical power for primary endpoint (one-sided $\alpha=2.5\%$ )	with 5% drop-out rate	with 10% drop-out rate	with 15% drop-out rate
1.65	3.0	90%	75%	79%	84%
1.65	3.0	80%	56%	59%	63%

SD=Standard Deviation

## 12.8.2 Secondary endpoint(s)

### Symptomatic dermographism

- Complete response rate

Assuming a type-I-error of 2.5% two-sided and a complete response (negative outcome in the FricTest®4.0) rate of 11% in the placebo group. With approximate 56 participants per group and a drop-out rate of 10%, the power to show a complete response rate of 44% in the ligelizumab groups based on Fisher's exact test (SAS 9.4, two group Fisher's-exact test of equal proportions) is 91.5%.

Placebo-response rates of 11% (2 out of 18) have been reported in [Maurer et al 2017](#).

The power of the all the endpoints included in the testing strategy is confirmed based on the simulation through the recycled alpha as planned. The detail simulation results will be provided in the statistical analysis plan.

### Cold urticaria

- Complete response rate

Assuming a type-I-error of 2.5% two-sided and a complete response (negative outcome in the TempTest®4.0) rate of 5% in the placebo group. With approximate 34 participants per group and a drop-out rate of 8%, the power to show a complete response rate of 40% in the ligelizumab groups based on Fisher's exact test (SAS 9.4, two group Fisher's-exact test of equal proportions) is 81.8%.

Placebo-response rates of 0% (0 out of 12) and 5% (1 out of 20) have been reported in [Metz et al 2017](#) and [Krause et al 2013](#), respectively.

The power of the all the endpoints included in the testing strategy is confirmed based on the simulation through the recycled alpha as planned. The detail simulation results will be provided in the statistical analysis plan.

### Cholinergic urticaria

- Complete response rate in itch NRS

For complete response in itch NRS, assuming a type-I-error of 5% two-sided and a complete response (see [Section 2.2](#)) rate of 13% in the placebo group. With approximate 79 participants per group and a drop-out rate of 10%, the power to show a complete response rate of 38% in the ligelizumab groups based on Fisher's exact test (SAS 9.4, two group Fisher's-exact test of equal proportions) is 91.1%.

In [Gastaminza et al](#), complete response rates of 22% (2 out of 9) and 8% (1 out of 13) have been reported for placebo and omalizumab 300 mg group during the blinded treatment period, and 37.5% (6 out of 16) in the overall population in the open label treatment period.

The power of the all the endpoints included in the testing strategy is confirmed based on the simulation. The detail simulation results will be provided in the statistical analysis plan.

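### The claim of at least 90% power does not hold for cholinergic complete response: in the fixed sequence it is about 82% to 86% even at the unsourced 13% placebo rate.

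*Protocol*

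**What the plan says.** Protocol Section 12.8.2 (Cholinergic urticaria) sets out the calculation for the first secondary endpoint, itch NRS = 0 at Week 12. It begins "assuming a type-I-error of 5% two-sided and a complete response" "rate of 13% in the placebo group". It continues "With approximate 79 participants per group and a drop-out rate of 10" per cent, and gives "the power to show a complete response rate of 38% in the ligelizumab groups" by Fisher's exact test as 91.1%.

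The next paragraph describes one omalizumab trial in cholinergic urticaria, in which "complete response rates of 22% (2 out of 9) and 8% (1 out of 13) have been reported" for placebo and omalizumab 300 mg respectively in the blinded period. The same trial had 37.5% (6 of 16) in its open-label period. No origin is given for the 13%.

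The other two cohorts each assume a placebo rate that they cite. For dermographism, "Placebo-response rates of 11% (2 out of 18) have been reported" and 11% is used. For cold urticaria, 0 of 12 and 1 of 20 are cited and 5% is used.

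Section 12.8 states that the sample sizes in all three cohorts are "sufficient to maintain the power of overall multiple testing strategy (at least 90" per cent) for the primary endpoint and the first secondary endpoint, through recycled alpha. SAP Section 3 repeats the claim, and SAP Section 3.1.2 repeats the 13% and the 91.1%.

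The testing strategy for cholinergic urticaria (Protocol Section 12.5, SAP Section 2.6.2) is a fixed sequence. "The initial alpha level is set to" 0.025 one-sided for the primary endpoint, and complete response in itch is tested at that level only if the primary is rejected. Section 12.8.1 gives the primary endpoint 90.2% power.

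**The concern.** There are two separate difficulties.

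The first is the input. This is the only cohort whose assumed placebo rate is not one of the rates it cites, and the departure is in the direction that raises power. Tables 12-3 and 12-4 vary only the primary-endpoint assumptions, drop-out and target power, so nothing shows how quickly 91.1% falls as the placebo rate rises.

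The second is the claim about the testing strategy. The 91.1% is the power of the Fisher test taken alone. In a fixed sequence the endpoint succeeds only if both tests succeed. Two tests with about 90% and 91% power taken singly would give at least 90% jointly only if almost every trial that won the first also won the second.

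At stake is whether the plan states correctly the chance of success for an alpha-controlled secondary endpoint. Type I error, the estimand and the analysis are not affected.

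**Working it through.** **Inputs.** 79 per arm with 10% drop-out gives 79 × 0.9 = 71.1, so n = 71 evaluable per arm. Alpha is 5% two-sided, used below as 2.5% one-sided. Complete response is 13% versus 38% (Section 12.8.2). For the primary endpoint the difference is 1.65 and the SD 3.0 (Section 12.8.1).

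**1. Reproduce the 91.1%.** The arcsine approximation to Fisher's test with continuity correction is

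power = Φ( √(2n) × [asin√(p₂ − 1/(2n)) − asin√(p₁ + 1/(2n))] − 1.96 ).

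With 1/(2n) = 0.00704:
- asin√0.37296 = 0.6570
- asin√0.13704 = 0.3792
- difference 0.2777; times √142 = 11.916 gives 3.310
- Φ(3.310 − 1.960) = Φ(1.350) = 91.1%

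Exact enumeration of all binomial outcomes gives 91.3%, the same at 5% two-sided and 2.5% one-sided. The stated figure is correct for its inputs.

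**2. Vary the placebo rate** (exact Fisher, n = 71 per arm, one-sided 2.5%, Fisher test taken alone).

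| Placebo | Ligelizumab | Power |
|---|---|---|
| 13% | 38% | 91.3% |
| 15% | 38% | 84.6% |
| 18% | 38% | 70.6% |
| 20% | 38% | 59.5% |
| 22% | 38% | 48.1% |
| 22% | 47% (25-point difference kept) | 85.0% |

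**3. Precision of the cited rate.** The exact 95% interval for 2/9 is 2.8% to 60.0%. If the true rate were 13%, two or more responders among nine would occur with probability 1 − 0.87⁹ − 9 × 0.13 × 0.87⁸ = 0.33.

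**4. Reproduce the primary power.** Noncentrality is (1.65/3.0) × √(71/2) = 0.55 × 5.958 = 3.277. On 140 degrees of freedom at one-sided 2.5% this gives 90.2%, as stated.

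**5. Power in sequence.** The required quantity is P(primary rejected and complete response rejected).
- Upper bound: min(90.2%, 91.3%) = 90.2%.
- Independent endpoints: 0.902 × 0.913 = 82.4%.
- Intermediate cases need an assumption, because the documents give no correlation. I simulated 100,000 trials per setting. Itch change was normal with SD 3 and a mean difference of 1.65. Complete response was obtained by cutting, at 13% or 38%, a normal variable with correlation ρ to improvement in itch. The t-test was followed by Fisher's test, each at one-sided 2.5%.

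| ρ | 13% vs 38% | 22% vs 38% | 22% vs 47% |
|---|---|---|---|
| 0 | 82.4% | 43.2% | 76.9% |
| 0.3 | 82.9% | 44.7% | 77.8% |
| 0.5 | 83.7% | 46.1% | 78.5% |
| 0.7 | 84.4% | 46.5% | 79.7% |
| 0.9 | 85.3% | 47.4% | 81.0% |
| 1.0 | 86.0% | 47.9% | 81.6% |

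The simulation error is about 0.1 to 0.2 percentage points. Both endpoints come from the same itch score, so the upper rows are the less realistic ones. For ρ of 0.3 or more the range at 13% versus 38% is about 83% to 86%.

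**The case against.** The arithmetic objection is right. The 91.1% follows from its stated inputs, so a reader who infers a miscalculation from the gap between 91.1% and 48% would be mistaken.

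A reader might also infer that the true power is 48%. The documents do not support that. The 22% is two participants out of nine and is compatible with 13%. The 48% also pairs a placebo rate from the blinded period with an active rate matching the open-label period; in the blinded period the active rate was lower than placebo. Protocol Sections 1.1 and 4.5 argue that ligelizumab may do better than omalizumab, so holding active at 38% is one choice among several. Keeping the 25-point difference gives 85%. It is also unclear that the cited rate carries over: the documents do not say how that trial defined complete response, and Section 12.8.1 describes its itch measure as a VAS.

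A third tempting inference is that 13% came from pooling the two blinded arms, 3/22 = 13.6%. That is a guess. The documents mention no pooling, and 13.6% would round to 14%.

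On the 90% claim, it can be said that Section 12.8 refers to endpoints taken singly, where 90.2% and 91.1% both pass, and that 13% is openly stated as an assumption. But the sentence speaks of the overall multiple testing strategy and of recycled alpha. For cholinergic urticaria there is one dose and a fixed sequence, so no alpha is recycled between doses, and the relevant power is the joint one. The Protocol defers detailed simulation results to the SAP; the published text of SAP Section 3 shows none.

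Finally, no cohort has a sensitivity table for a secondary endpoint, and the trial stopped early with 39 enrolled. Both are true. They limit the point to the design justification.

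**Conclusion.** The concern holds in two parts.

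The 91.1% is correct but marginal, and it depends on an unsourced placebo rate more favourable than the only cholinergic rate cited. An increase of two percentage points in that rate takes it below 85%. The 22% case shows sensitivity and is not an estimate of the trial's power.

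The claim of at least 90% does not hold for this endpoint even on the plan's own inputs. Power to win both tests is bounded by 90.2% and is about 82% to 86% for correlations from 0 to 1, given 71 evaluable per arm, normal itch changes and the latent-variable link described above. The bound and the independence value need no simulation; the values between them depend on that link. At 22% versus 38% the figure is at most about 48%, whatever the correlation.

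SAP Section 4 states that no statistical analyses will be performed on the primary or secondary endpoints, so no reported result depends on this.

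**What to change.** In Protocol Section 12.8 and SAP Section 3, withdraw the claim of at least 90% for cholinergic complete response. Replace it with the power in sequence: about 82% to 86% at 13% versus 38%, identified as a range over assumed correlations between the two endpoints. Add that it falls to at most about 48% at the cited 22% if active stays at 38%. A sentence giving the origin of the 13% in Section 12.8.2 would help but is optional.

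The sample size of 79 per arm and the analysis need no change. The only cost is a less favourable stated figure.
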